8.2.3.2. Other Safety Assessments

Pfizer standard safety data presentations will be made for demography data, discontinuation data, adverse event data, laboratory test data, vital signs data and ECG data.

For the 3-tier adverse event reporting, tier 1 adverse events are defined in the tanezumab Safety Review Plan, and this definition of tier-1 adverse events for the report of study 1058 tables will be finalized prior to the unblinding of this study.

Tier 2 AEs are those with a frequency of $\geq 3\%$ in any treatment group.

Tier 3 AEs are those not in tier 1 or tier 2, and will be summarized using standard Pfizer data standards tables, where all Adverse Events will be included (ie, tier 3 AEs will not be shown separately).

Adverse events within tier 1 and 2 will be summarized using Risk Differences between each tanezumab group and NSAID, together with 95% confidence intervals, using exact methods. Significance tests will be performed for tanezumab versus NSAID comparisons using exact methods for the tier 1 adverse events. There will be no multiplicity adjustment for these significance tests. These tables will be produced for the comparisons of tanezumab 2.5 mg versus NSAID and tanezumab 5 mg versus NSAID.

The following footnote will be used in the Tier 1 AE tables: “P-values and confidence intervals are not adjusted for multiplicity and should be used for screening purpose only. 95% CIs are provided to help gauge the precision of the estimates for Risk Difference. Risk Difference is computed as ‘Tanezumab 5 mg versus NSAID’ and ‘Tanezumab 2.5 mg versus NSAID’. Exact methods are used for 95% confidence intervals and significance tests.”

Similarly the following footnote will be used in the Tier 2 AE tables: “Confidence intervals are not adjusted for multiplicity and should be used for estimation purposes only. 95% CIs are provided to help gauge the precision of the estimates for Risk Difference. Risk Difference is computed as ‘Tanezumab 5 mg versus NSAID’ and ‘Tanezumab 2.5 mg versus NSAID’. Exact methods are used for 95% confidence intervals.”

It should be recognized that most studies are not designed to reliably demonstrate a causal relationship between the use of a pharmaceutical product and an adverse event or a group of adverse events. Except for select events in unique situations, studies do not employ formal adjudication procedures for the purpose of event classification. As such, safety analysis is generally considered as an exploratory analysis and its purpose is to generate hypotheses for further investigation. The 3-tier approach facilitates this exploratory analysis.

All summaries of adverse events will be shown for adverse events that begin or worsen after the first dose of SC study drug (treatment-emergent) up to the end of the treatment period. In addition a selection of adverse event tables will be produced for the safety follow-up period and for the whole period up to the end of the study, including the treatment period and safety follow-up period.

090017764937816561ApprovedApproved On: 03-10-2019 08:56 (GMT)

Adverse events (AEs), concomitant medications, laboratory safety tests, physical and neurological examinations (NIS), vital signs, electrocardiogram (ECG), and the ADA test will be collected for each subject during the study according to the schedule of assessments.

The following non-standard safety tables will also be included

1. A summary of baseline characteristics, including Kellgren-Lawrence grade of the index joint (for subjects with Hip and Knee OA separately and then overall), highest Kellgren-Lawrence grade for each subject, Summary of WOMAC subscales at Baseline and Screening (for Pain subscale only), diabetes status (from medical history and/or pre-treatment HbA1c \geq 6.5%), and the PGA at Baseline. This summary will also include a summary of the number of subjects who are \geq 75 years old.
2. Summary of number of subjects treated by country and treatment group, and by NSAID cohort.
3. Summary of failed drug treatments for protocol qualification, with reasons for discontinuation.
4. Incidence and severity of AEs leading to discontinuation.
5. Summary of AEs, Incidence of AEs, Incidence of AEs leading to discontinuation and summary of Serious AEs will be shown for the whole study period (including the safety follow-up period).
6. Summary of AEs and Serious Adverse Events by 1000 patient years of exposure.
7. Summary of evidence of neurological examination abnormalities by visit and final assessment, and incidence of neurological findings over consecutive visits. Further details of this summary are given below.
8. Summary of final outcome of neurological consultation.
9. Summary of the Incidence of sympathetic neuropathy based on investigator assessment and, if performed, expert consultant assessment.
10. 'Incidence and severity' tables of treatment-emergent AEs of Abnormal Peripheral Sensation (APS) and Sympathetic Nervous Function, as defined above. Other adverse events may be added to these groupings if they are observed in this study or other studies in the tanezumab program.
11. Summary table and listing of inclusion and exclusion criteria that are not met by subjects who were screened (but not randomized).
12. Summary of discontinuation by treatment group and reason, and study week of discontinuation for the treatment period (Weeks 1-2, 3-4, 5-8, 9-12, 13-16, 17-24, 25-32, 33-40, 41-48, 49-56, >56) and for the safety follow-up period (Weeks 1-8, 9-16, 17-24, >24).

0900177e41931781b0561Approved\Approved On: 03-Oct-2019 08:56 (GMT)

13. A summary of the maximum increase from baseline in the sitting systolic and diastolic blood pressure. The categories used are: (systolic BP) only decreases or no change, >0 to 10, >10-20, >20-30, >30, and (diastolic BP) only decreases or no change, >0 to 10, >10-20, >20.
14. A summary of the maximum decrease from baseline in the sitting systolic and diastolic blood pressure. The categories used are: (systolic BP) <-30, -30 to <-20, -20 to <-10, -10 to <0, only increases or no change, and (diastolic BP) <-20, -20 to <-10, -10 to <0, only increases or no change.
15. A summary of the change from baseline to last observation in the sitting systolic and diastolic blood pressure. The categories used for these summaries are: (systolic BP) \leq -40, >-40 to -30, >-30 to -20, >-20 to -10, >-10 to 0, >0 to <10, 10-<20, 20-<30, 30-<40, \geq 40, and (diastolic BP) \leq -30, >-30 to -20, >-20 to -10, >-10 to 0, >0 to <10, 10-<20, 20-<30, \geq 30.
16. A summary of incidence of subjects with confirmed orthostatic hypotension, for each visit and any post-baseline incidence of orthostatic hypotension.
17. A summary of discontinuation up to End of Treatment period, and up to End of Study period.
18. Incidence of musculoskeletal physical examination findings at screening.
19. Summary of Dual Energy X-Ray Absorptiometry (DEXA) at screening, showing summary measures of bone mineral density, and t-scores of the spine and hip.
20. Summary of the Survey of Autonomic Symptoms (SAS) number of symptoms reported and total symptom impact score, at each visit, and for the change from Baseline score.
21. Summary of concomitant medications for Osteoarthritis for non-NSAID and NSAID medications (shown separately).
22. Summary of number of days of non-study NSAID use per dosing interval (eg, Day 1 to Week 8, Week 8 to Week 16, etc.) and for the first 8-week interval in the safety follow-up period. This will show the number and percentage of subjects in an interval who exceeded the limit of 10 days of NSAID use. If an interval exists, the visits will be used to define the interval, otherwise calendar time will be used. A summary of average number of days of NSAID use will be displayed by interval. Also, a summary of the overall number of days of NSAID use from Day 1 to Week 64 will be shown, as well as the number and percentage of subjects who exceeded the limit of 80 days of NSAID use during this interval.

09001776e1931781b656\Approved\Approved On: 08-10-2019 08:56 (GMT)

23. Summary of oral study medication compliance. This is calculated for the interval from Baseline to Week 16 and the entire post-Baseline period up to Week 56 (or end of treatment visit). Compliance is calculated as number of tablets dispensed minus the number returned divided by the number of days in the interval, all divided by 2 (for the daily regimen frequency), multiplied by 100, to get a percentage compliance for each subject for each time period.

Neurological-related safety data

The “conclusion from the neurological examination” data will be summarized for each time point and the last subject assessment. In addition the persistence of any neurological examination finding will be summarized, showing the incidence of subjects with new or worsened neurological examination abnormalities (both clinically significant only and also for any finding) for 2, 3, 4, and ≥ 5 consecutive visits.

Immunogenicity

The following assessments of ADA data will be made:

- A listing of individual serum ADA results sorted by treatment group, subject ID and planned visit. The listing will also include the actual test date/times.
- The proportion of subjects who test positive (ie, develop anti-tanezumab antibodies) and negative will be summarized by treatment group and planned visit. The summary will also include the proportion of subjects who test positive and negative overall in the study.
- Subjects who develop anti-tanezumab antibodies after treatment will be evaluated for the presence of anti-tanezumab neutralizing antibodies, and individual results will be listed.
- Individual subjects with positive ADA results will be evaluated for potential ADA impact on the individual’s PK, efficacy and safety profile.

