Tanezumab 2.5 mg, 5 mg, or placebo for tanezumab will be administered as a SC injection and subjects will be observed for adverse events including signs and symptoms of hypersensitivity in the clinic for a minimum of 1 hour after each administration of investigational product. Subjects will take their first oral dose of NSAID (naproxen 500 mg BID, celecoxib 100 mg BID, or diclofenac ER 75 mg BID) or matching placebo of the Double-blind Treatment period in the evening on Day 1 (ie, a morning dose of oral double-blind, investigational product will not be taken). Additional administrations of SC investigational product will occur every 8 weeks following the Baseline (Day 1) administration through Week 48. Oral investigational product (NSAID or matching placebo) will be self-administered by subjects BID through Week 56 of the study. Efficacy, activity level and safety assessments will be conducted during clinic visits between Weeks 2 and 64. In addition, subjects will be contacted by telephone every 8 weeks between Weeks 12 and 60 and every 4 weeks between Weeks 64 and 80 (ie, Weeks 68, 72 and 76).

At the Week 16 visit, subjects must have a 30% or greater reduction in WOMAC Pain subscale relative to Baseline in the index joint and a 15% or greater reduction in WOMAC Pain subscale from Baseline at either Week 2, 4 or 8 in order to continue investigational product. Subjects who do not meet these response criteria will be discontinued from the Treatment Period and enter the 24-week Early Termination Follow-up period.

At Weeks 24, 56, and 80, all subjects will undergo repeat radiographs of each knee, hip and shoulder as well as any additional joint(s) that was imaged at Screening. At Week 24, confirmation of the continuing radiographic eligibility of subjects must be received from the Central Reader prior to administration of the Week 24 SC investigational product. Subjects with Kellgren-Lawrence Grade 3 or 4 osteoarthritis in any knee or hip joint, on the basis of the Central Reader's assessment of the screening X-rays, will have follow-up MRIs of each hip and knee obtained at Weeks 24, 56, and 80.

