8.1.3. Analyses for Binary Endpoints

Binary response parameters, and the incidence of rescue medication use and treatment discontinuation due to lack of efficacy will be analyzed using logistic regression for binary data, with covariates described in Section 6.4. Output will show the number and percentage of subjects in each response category, and odds ratios (with 95% CIs) for the treatment comparisons shown in Section 4.1.

Separate analyses of the joint safety endpoints will use exposure time as the denominator (giving results in terms of events per 1000 patient years of exposure) and then number of subjects as the denominator (giving results in terms of percentages). Both these analyses will be performed for risk difference and risk ratio. The analyses using number of subjects as the denominator will analyze risk difference and ratio between both tanezumab groups and NSAID using exact methods. The analyses using exposure as the denominator will analyze risks using Poisson models. The model for risk difference will have a linear link, poisson errors, and model terms for exposure and exposure-by-treatment (where treatment is 1 for tanezumab group and 0 for NSAID). The model for risk ratio will have a log-link, poisson errors, and model term for treatment group with log-exposure as the offset variable.

Results will show event rates by treatment group, and difference/ratio of tanezumab doses versus NSAID, all shown with 95% confidence intervals, and significance tests for the treatment comparisons.

Events will be included in summaries if they occur up to the end of the safety follow-up period or 26 weeks (planned duration of the follow-up period + 2 weeks) after the end of the treatment period, whichever is later.

For the joint safety event analyses, the observation period is defined as the time from first SC dose to study completion or discontinuation for subjects who did not have an event, or time from first SC dose to the earliest event for subjects who did have at least one event.

0900177ed193181b656Approved\Approved On: 08-10-2019 08:56 (GMT)

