The response endpoints of OMERACT, improvement in PGA ≥ 2 and WOMAC Pain and Physical Function ≥ 30 , 50, 70 and 90% improvements are analyzed using logistic regression with covariates of Baseline score (WOMAC Pain for OMERACT), Baseline diary average pain, Index Joint, Highest KL grade (2, 3 or 4), NSAID cohort and Treatment Group, for response at Weeks 2, 4, 8, 16, 24, 32, 40, 48, and 56. These analyses use mixed BOCF/LOCF, and BOCF and LOCF for missing data. The use of BOCF for missing data implies subjects with missing data are included in the analysis as non-responders. Similarly the use of LOCF in the case where subjects have no post-Baseline data (and Baseline would be carried forward) again implies those subjects are included in the analysis as non-responders.

09001776e493781b6561Approved\Approved On: 04-Oct-2019 08:56 (GMT)

Incidence of rescue medication use will be analyzed using the logistic regression as described above up to Week 56, but only using LOCF imputation for missing data.

The incidence of treatment discontinuation due to lack of efficacy will be analyzed using logistic regression with model terms of Baseline WOMAC Pain, Baseline diary average pain, the three stratification parameters and treatment group, and using incidence up to the end of treatment period (the Week 56 visit or early termination). Discontinuation in the post-treatment safety follow-up period will not be included in this endpoint for analysis, but will be summarized as part of the safety tables. Lack of efficacy is indicated as ‘Insufficient Clinical Response’ on the Subject Summary Case Report Form. An additional analysis will be performed also including the discontinuation reason of ‘Patient meets protocol specified pain criteria for discontinuation’.

The cumulative WOMAC Pain and Physical Function response at Weeks 16, 24 and 56 using response definitions from a reduction of >0% to =100% (in steps of 10%) will be summarized, using mixed BOCF/LOCF, and also LOCF and BOCF imputation. Imputation with BOCF for subjects with missing data at that time point will lead to the subjects being assessed as non-responders for the response endpoint.

4. Time to Event.

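### Tier 1 and Tier 2 adverse-event risk differences appear to rest on crude percentages over unequal treatment periods; an exposure-adjusted risk difference should stand beside them

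*SAP*

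**What the plan says.** SAP Section 8.2.3.2 compares Tier 1 and Tier 2 adverse events between each tanezumab dose and NSAID by risk difference with exact 95% intervals. Tier 1 is also tested: "Significance tests will be performed for tanezumab versus NSAID comparisons using exact methods for the tier 1 adverse events". The AE tables cover "adverse events that begin or worsen after the first dose of SC study drug (treatment-emergent) up to the end of the treatment period".

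The section does not state the denominator. SAP Section 8.1.3, written for the joint safety endpoints, pairs method with denominator: "The analyses using number of subjects as the denominator will analyze risk difference and ratio between both tanezumab groups and NSAID using exact methods". It reserves Poisson models for rates over exposure. By analogy, exact methods for Tier 1 and Tier 2 imply subject counts.

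Nor does the SAP say, for AE tables, when the treatment period ends in someone who stops early. The nearest wording concerns discontinuation for lack of efficacy in SAP Section 8.2.2: "using incidence up to the end of treatment period (the Week 56 visit or early termination".

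Protocol Section 3 sets the Week 16 rule: "subjects must have a 30% or greater reduction in WOMAC Pain subscale relative to Baseline in the index joint", together with a smaller early response. It continues: "Subjects who do not meet these response criteria will be discontinued from the Treatment Period and enter the 24-week Early Termination Follow-up period".

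The SAP does plan a descriptive table of AEs and SAEs per 1000 patient-years, selected whole-study and follow-up AE tables, and discontinuation by arm, reason and week. Tier 1 p-values carry a footnote restricting them to screening. For the primary joint safety endpoint, SAP Section 8.2.3.1 makes the exposure-adjusted risk difference the primary analysis.

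**The concern.** The rule that shortens AE observation is a threshold on WOMAC Pain, a co-primary efficacy outcome. The sample size assumes that tanezumab beats NSAID on that outcome, so the plan's own hypothesis implies that more tanezumab subjects remain in the AE tables from Week 16 to Week 56. Where risk continues after Week 16, a crude percentage then mixes event risk with time observed.

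Two things follow. An AE with the same hazard in all arms shows, in expectation, a small excess on tanezumab. A real NSAID excess is diluted: with the inputs below and a 10% event, a true hazard ratio of 0.90 in favour of 5 mg appears as a crude risk ratio of about 1.00. Tier 1 holds the events of most interest and is the only AE tier tested, so its tables are where a reader would look for such signals.

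**Working it through.** **Check of the plan's inputs.** Protocol Section 9.1 gives 80% power with about 220 per group for a WOMAC Pain difference of -0.73 and SD 2.73. SE = 2.73 × √(2/220) = 0.260; 0.73/0.260 = 2.80; Φ(2.80 − 1.96) = 0.80. The figure reproduces, so the difference and SD are used as they stand.

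**Inputs.** From Protocol Section 9.1: SD 2.73, differences -0.73 (5 mg) and -0.45 (2.5 mg), 1000 per arm. Assumed: baseline pain 7 (Protocol Section 1.2.3.1 reports means above 7 in earlier studies), NSAID mean change -2.5, the same constant AE hazard in all arms, and observation of 16 weeks for non-responders and 56 for responders. The early-response condition and other dropout are not modelled. No Tier 1 event rate is given in the documents, so the rate is varied.

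**Share passing the 30% rule** = Φ((mean reduction − 0.3 × 7)/2.73):
- NSAID: Φ(0.40/2.73) = 56%
- 2.5 mg: Φ(0.85/2.73) = 62%
- 5 mg: Φ(1.13/2.73) = 66%

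**Mean observation** = 16 + 40 × share: 38.3, 40.9 and 42.4 weeks. The ratio to NSAID is 1.07 for 2.5 mg and 1.11 for 5 mg. Anchoring instead on a 3.0 to 3.3 point reduction on 5 mg, with baseline 6.5 to 7.5, gives 1.06 to 1.07 and 1.10 to 1.12.

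**Crude incidence** = r × p56 + (1 − r) × p16, where r is the passing share and p16 = 1 − (1 − p56)^(16/56). For p56 = 10%, p16 = 2.97%:
- 5 mg: 0.661 × 10% + 0.339 × 2.97% = 7.6%
- NSAID: 0.558 × 10% + 0.442 × 2.97% = 6.9%
- Difference 0.7 points, ratio 1.10

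**False-positive probability.** The SAP names no particular exact test, so two-sided Fisher at 5% is assumed and enumerated over both binomials with 1000 per arm:

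| 56-week incidence | Total, equal observation | Total, 5 mg v NSAID | Total, 2.5 mg v NSAID | False excess on 5 mg |
|---|---|---|---|---|
| 10% | 4.1% | 8.1% | 5.7% | 2.0% → 7.7% |
| 5% | 3.8% | 5.7% | 4.5% | 1.9% → 5.0% |
| 3% | 3.4% | 4.4% | 3.8% | 1.7% → 3.7% |
| 1% | 2.6% | 2.9% | 2.7% | 1.3% → 2.1% |

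**With exposure adjustment.** At equal constant hazard (10% over 56 weeks), first events over patient-years give 98.2 per 1000 patient-years in both arms, so the rate difference is zero.

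**When events come early.** If every event falls before Week 16, the crude ratio is 1.00 and the rate ratio on mean observation time is 38.3/42.4 = 0.90. If half of a 10% event falls by Week 16 (p16 = 5%), crude incidence is 8.3% v 7.8%, a ratio of 1.07, and the rate ratio is 1.07 × 0.90 = 0.96.

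**Whole-study percentages.** Week 16 stoppers, last dosed at Week 8, are followed to about Week 32 and completers to Week 80. The crude ratio for the same hazard is 11.2%/10.4% = 1.08, so these tables reduce the imbalance without removing it.

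**The case against.** The strongest case against has four parts.

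- **Status.** The Tier 1 p-values are labelled for screening only, and the SAP calls safety analysis exploratory. No decision rests on the 5% level. This stands and lowers the weight of the point. But the footnote warns about multiplicity, not about unequal observation time, so it does not tell a reader how to interpret a small excess.
- **Estimand.** The percentage with an event during treatment, under a regimen that includes its response rule, is a legitimate quantity. This stands, and is a reason to keep it.
- **Existing tables.** The per-1000-patient-year summary and the discontinuation tables make unequal exposure visible. This stands in part: no exposure-adjusted risk difference or interval is specified for Tier 1 or Tier 2.
- **A rate has its own bias.** When events cluster before Week 16, rates favour the better-retained arm, here by a ratio of about 0.90, and could mask harm on tanezumab. This stands in full.

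A reader might therefore infer that the rate should replace the crude risk difference as the tested quantity. The documents do not support that: no event timing is given, and each measure misleads under a different timing. A reader using a normal approximation might also put the total error for a 10% event near 9.5%; the SAP specifies exact methods, and Fisher's test gives 8.1%.

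**Conclusion.** The point holds as a modest gap in presentation. At equal constant hazards, the planned Tier 1 and Tier 2 comparisons lean against tanezumab by about 10% in relative terms for 5 mg and about 7% for 2.5 mg. That is about 0.7 percentage points for 5 mg at 10% incidence and under 0.4 points at 5% or below. For 5 mg the total false-positive rate exceeds 5% clearly at 10% incidence, slightly at 5%, and not at 3% or 1%.

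This rests on the plan's assumed efficacy, the illustrative baseline and NSAID response, and two inferences: subject counts as the denominator, and early termination as the end of the AE window.

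Two stronger readings should be set aside. A reader might infer that AE counting stops at Week 16 for non-responders. Only the treatment-period tables stop; Protocol Section 8.2 records AEs through the last visit. A reader might also infer that the better-retained arm must show more events. That holds only in expectation, and only if retention differs, hazards are equal and risk continues after Week 16.

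**What to change.** In SAP Section 8.2.3.2:

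- Keep the crude exact risk difference, its interval and the Tier 1 screening p-value.
- Beside them, for Tier 1 and Tier 2, add an exposure-adjusted risk difference with 95% CI: subjects with a first event over patient-years to first event or end of treatment period, by the Poisson method already specified for joint safety in Section 8.1.3.
- State the denominator of the crude measure, and when the treatment period ends in the AE tables for subjects who stop early.
- Add a footnote: crude percentages reflect unequal observation time after the Week 16 rule; rates assume a roughly constant hazard and can favour the better-retained arm when events cluster early; the two should be read together.

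The cost is SAP wording and extra table columns. Exposure is already needed for the per-1000-patient-year table, and no new data are collected. The downside is busier tables and a constant-hazard assumption that will not suit every event.
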